#### **Management in the clinical guidelines arm:**

The children will be treated as directed by their Consultant Paediatrician. The prescription for the drugs to be used will be dispensed from the pharmacy department at the Royal Brompton Hospital – as directed by the clinician. Usually only 2 weeks of medication is prescribed by the pharmacy, but for this trial 4 months' supply will be given.

#### **6.2 Dose modifications for toxicity**

All drugs to be used in the trial are already licenced for use in children of this age and in the doses to be used. Drug induced toxicity is therefore not a concern.

#### **6.3 Premedication**

There are no additional drugs that will be used before randomisation.

#### **Concomitant treatment**

The following medication will be allowed to continue during the intervention period in both study arms.

1. Use of rescue medication with bronchodilators for acute symptoms – salbutamol and/or ipratropium bromide
2. Use of leukotriene receptor antagonist – montelukast – can continue regardless of whether it is being taken regularly or as required for acute symptoms

#### **6.4 Interaction with other drugs**

All drugs to be used are already licenced for use in children of this age. There are no other drugs that the child should not receive while they are in the trial and having the drug interventions for the trial.

#### **6.5 Dispensing and Accountability**

The following drugs will be sourced from routine hospital stock and their handling and management will be subject to standard procedures of the pharmacy.

Beclometasone dipropionate metred dose inhaler with spacer – 100mcg per dose

Augmentin duo syrup

Azithromycin syrup

The Pharmacy hospital department will be responsible for maintaining & updating the trial Accountability Log, filed in the hospital pharmacy file.

#### **Route of administration, dosage, dosage regimen, and treatment period(s) of the medications**

Beclometasone dipropionate – inhaled, 100 mcg – 2 puffs twice daily via mdi and spacer, for 4 months

Augmentin duo – oral, 0.3ml/kg twice daily for 4 weeks

Azithromycin – oral 10mg/kg once daily for 4 weeks

#### **Assessment of compliance**

All beclometasone inhalers will be fitted with an electronic monitoring device (Smartinhaler) in order to ensure the medication has been taken according to the regimen prescribed

The antibiotic for the full 4 week period will be dispensed from the hospital to help compliance

Parents will be phoned weekly to remind them of the importance of giving the child's treatment – whether that is the inhaler or antibiotics.

## **7. PHARMACOVIGILANCE**

### **7.1 Definitions:**

**Adverse Reaction (AR):** all untoward and unintended responses to a medication related to any dose administered. *All AEs judged by either the reporting investigator or the sponsor as having reasonable causal relationship to a medicinal product qualify as adverse reactions.*

**Unexpected Adverse Reaction:** an AR, the nature or severity of which is not consistent with the applicable product information (eg investigator's brochure for an unapproved investigational product or summary of product characteristics (SmPC) for an authorised product).

**Serious Adverse Event (SAE) or Serious Adverse Reaction:** any untoward medical occurrence or effect that at any dose:

### **Results in death**

**Is life-threatening** – refers to an event in which the subject was at risk of death at the time of the event; it does not refer to an event which hypothetically might have caused death if it were more severe

**Requires hospitalisation, or prolongation of existing inpatients' hospitalisation**

**Results in persistent or significant disability or incapacity**

**Is a congenital anomaly or birth defect**

An Unexpected Adverse Reaction is an Adverse Reaction, when both the nature and severity of the event is not consistent with the information about the medicinal product in question,

- (a) in the case of a product with a marketing authorization, in the Summary of Product Characteristics (SmPC) for that product.

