### **Terminology for classification of SAEs**

**1. Severity** will be described using the following categories:

- **Mild**—the adverse event does not interfere with the volunteer's daily routine, and does not require intervention; it causes slight discomfort.
- **Moderate**—the adverse event interferes with some aspects of the volunteer's routine, or requires intervention, but is not damaging to health; it causes moderate discomfort.
- **Severe**—the adverse event results in alteration, discomfort or disability which is clearly damaging to health.

**3. Expectedness** will be described using following categories:

- **Expected**—an AE that is classed in nature as serious and which is consistent with the information about the drug listed in the SmPC.
- **Unexpected**—an AE that is classed in nature as serious and which is not consistent with the information about the drug listed in the SmPC.

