### **Recording of Safety Information**

Collection, recording and reporting of AEs (including serious and non-serious events and *reactions*) to the Sponsor will be done according to the Sponsor's Pharmacovigilance SOP.

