#### ***Adverse Events (AEs)***

All Adverse Events will be recorded in the hospital notes in the first instance.

A record of all AEs, whether related or unrelated to the treatment will also be kept in the CRF and the Sponsor's AE Log.

All drugs used in this trial are licensed in the UK and used within their marketing authorization.

The most up-to-date version of the SmPC will be used during the trial.

Contact details for reporting SAEs and SUSARs:

[contact], attention [name]

Please send SAE forms to: [name]

[contact] [name]

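### Section 7.1 defines an unexpected adverse reaction twice with conflicting logic (nature *or* severity, then *both*), and the protocol does not say which applies

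*Combined protocol and SAP*

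**What the plan says.** Section 7.1 (Definitions) defines an unexpected adverse reaction as "an AR, the nature or severity of which is not consistent with the applicable product information". For an authorised product, that information is the summary of product characteristics (SmPC).

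Further on in the same section, after the seriousness criteria, the term is defined again. A reaction is now unexpected "when both the nature and severity of the event is not consistent with the information about the medicinal product in question", and for a product with a marketing authorisation the reference is again the SmPC.

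The part headed Terminology for classification of SAEs adds a third wording. Its category *Unexpected* is "an AE that is classed in nature as serious and which is not consistent with the information about the drug listed in the SmPC", and *Expected* is the mirror image. Severity is graded there as mild, moderate or severe, with no link to expectedness.

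Two further places bear on the consequence:

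- Recording of Safety Information states that collection, recording and reporting of adverse events to the sponsor "will be done according to the Sponsor's Pharmacovigilance SOP". The procedure itself is not reproduced.
- Adverse Events (AEs) has every event entered in the hospital notes, the CRF and the sponsor's log, whether or not it is related to treatment. It also contains the line "Contact details for reporting SAEs and SUSARs", the only place in the supplied text where SUSARs are mentioned.

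**The concern.** A definition of this kind is a classification rule, and it should return one answer for each reaction. Here *or* in one sentence becomes *both ... and* in the other, and no text ranks one above the other. Two people following the protocol faithfully could label the same reaction differently.

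Expectedness is what separates a SUSAR from other serious reactions suspected to be related to treatment. If the second sentence were applied as written, a serious reaction that is listed in the SmPC but occurs in a more severe form than listed would be called expected. The children are aged 1 to 5 years, and in the pathological phenotype arm they may receive a 4-week antibiotic course or 4 months of inhaled steroid. All these products are licensed, so many of their reactions will already be listed, and listed nature with greater severity is a natural disputed case.

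**Working it through.** No arithmetic applies. The check sets the wordings side by side.

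**Step 1: do the two definitions cover the same reactions?** The first allows for an investigator's brochure or an SmPC, depending on the product. The second uses the SmPC for a product with a marketing authorisation. The protocol states that all trial drugs are licensed in the UK (Adverse Events), so for this trial both point to the SmPC. They cannot be reconciled by assigning them to different products.

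**Step 2: apply both rules to each combination.** Let N mean that the nature is inconsistent with the SmPC, and S that the severity is. The first definition is N *or* S. The second, read plainly, is N *and* S.

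| Nature vs SmPC | Severity vs SmPC | First definition | Second definition |
|---|---|---|---|
| consistent | consistent | expected | expected |
| consistent | inconsistent | **unexpected** | **expected** |
| inconsistent | consistent | **unexpected** | **expected** |
| inconsistent | inconsistent | unexpected | unexpected |

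The rules disagree in 2 of the 4 rows. Whenever N *and* S holds, N *or* S holds too, so the second rule can only reduce the number of reactions called unexpected.

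**Step 3: how firm are the two disagreements?** The second row is clear-cut: the reaction is listed, its severity goes beyond the listing, and the rules part. The third row depends on how severity is judged when the SmPC does not list the reaction at all. An assessor who holds that an unlisted reaction is automatically inconsistent in severity would move it to the fourth row. An assessor who does not would call an unlisted reaction expected under the second rule. The protocol does not address this.

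**Step 4: does the third wording settle it?** The *Expected* and *Unexpected* categories turn on consistency with the SmPC, without saying whether severity is part of it. The word *nature* does appear, but it is attached to the event being serious, not to the kind of reaction. The wording contains no *both*, so it sits somewhat more easily with the first definition, but it does not decide the second row.

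**The case against.** The wording conflict is hard to dispute, but there is a fair case that little follows from it.

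- **The sponsor's procedure governs reporting.** It may contain the wider definition and be what is used in practice. This stands as a limit on the consequence. It does not remove the conflict, because the procedure is not in the documents and the protocol does not say that it overrides section 7.1.
- **Expectedness does not decide what is recorded.** All adverse events go into the CRF and the sponsor's log, and there is a route for SAE forms. A serious reaction labelled expected would therefore still be recorded for the sponsor. This stands: what could be affected is onward reporting, and only if the label given under the second sentence is final.
- **The second sentence may be loose drafting.** It could be meant as *not both consistent*, which would agree with the first definition. That reading is possible but not the natural one. If it is what was intended, the correction changes nothing that was meant.
- **The text may be incomplete here.** The contents list has entries for causality (7.2) and reporting procedures (7.3) that do not appear as headings in the supplied text, and the SAE terminology jumps from item 1 to item 3. No fault is inferred from that, but a clarifying rule could lie there.

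A reader might go further and infer that SUSARs will be missed because investigators classify from the protocol's definitions. The documents do not support this. Section 7.1 names the reporting investigator or the sponsor only as judges of causal relationship. Nothing says who decides expectedness or from which text. SUSARs appear only in a contact line, with no visible definition or timeline.

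**Conclusion.** The point holds as a conflict between two current definitions in section 7.1. They give different answers in two of four nature and severity combinations, and in both the later sentence is the less protective. The third wording does not resolve it. This rests on the plain reading of *both ... and*. For the unlisted reaction, it also rests on its severity not being treated as automatically inconsistent.

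The consequence is conditional. Under-classification of SUSARs could occur if the later sentence is the one applied and the sponsor's procedure does not correct it. The documents do not show whether either condition is met, and they give no basis for a rate. The matter is confined to safety classification: the sample size, the primary endpoint and the analysis are untouched. It should be corrected because it is a safety rule that conflicts with its own counterpart as written, and the correction is nearly free.

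**What to change.** In section 7.1, either delete the second definition (the sentence after the seriousness criteria, with its SmPC item) or change its condition from *both the nature and severity* to *the nature or severity*. One definition, matching the one already given at the start of the section, then applies throughout.

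Optionally, align the SAE terminology to it: *Expected* would mean consistent with the SmPC in nature and severity, and *Unexpected* would mean not consistent in nature or severity. This is a clarification; the contradiction is removed without it.

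The cost is a few words in section 7 and possibly slightly more reactions classed as unexpected.

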### **Terminology for classification of SAEs**

**1. Severity** will be described using the following categories:

- **Mild**—the adverse event does not interfere with the volunteer's daily routine, and does not require intervention; it causes slight discomfort.
- **Moderate**—the adverse event interferes with some aspects of the volunteer's routine, or requires intervention, but is not damaging to health; it causes moderate discomfort.
- **Severe**—the adverse event results in alteration, discomfort or disability which is clearly damaging to health.

**3. Expectedness** will be described using following categories:

- **Expected**—an AE that is classed in nature as serious and which is consistent with the information about the drug listed in the SmPC.
- **Unexpected**—an AE that is classed in nature as serious and which is not consistent with the information about the drug listed in the SmPC.

### **Recording of Safety Information**

Collection, recording and reporting of AEs (including serious and non-serious events and *reactions*) to the Sponsor will be done according to the Sponsor's Pharmacovigilance SOP.

#### ***Adverse Events (AEs)***

All Adverse Events will be recorded in the hospital notes in the first instance.

A record of all AEs, whether related or unrelated to the treatment will also be kept in the CRF and the Sponsor's AE Log.

All drugs used in this trial are licensed in the UK and used within their marketing authorization.

The most up-to-date version of the SmPC will be used during the trial.

Contact details for reporting SAEs and SUSARs:

[contact], attention [name]

Please send SAE forms to: [name]

[contact] [name]

#### **Annual Progress Reports (APRs)**

The Chief Investigator will prepare the APR. It will be reviewed by the JRO and sent to the main REC within 30 days of the anniversary date on which the favourable opinion was given by the Ethics committee, and annually until the trial is declared ended.

#### **Notification of Serious Breaches of GCP and/or the protocol**

Any Protocol Deviations, Violations, Potential Serious Breaches and Urgent Safety Measures will be recorded using the Sponsor's Log issued during the Sponsor's Trial/Site Initiation meeting/visit.

Regulation 29A of the Medicines for Human Use (Clinical Trials) Regulations2004 [Statutory Instrument 2004/1031], as amended by Statutory Instrument2006/1928, contains a requirement for the notification of "serious breaches" of GCP or the trial protocol:

(1) The Sponsor of a clinical trial shall notify the licensing authority in writing of any serious breach of:

(a) The conditions and principles of GCP in connection with that trial; or

(b) the protocol relating to that trial, as amended from time to time in accordance with regulations 22 to 25, within 7 days of becoming aware of that breach.

(2) For the purposes of this regulation, a "serious breach" is a breach which is likely to effect to a significant degree:

(a) The safety or physical or mental integrity of the subjects of the trial; or

(b) The scientific value of the trial.

The Sponsor will be notified immediately of any case where the above definition applies during the trial conduct phase. The Sponsor's SOP on the Protocol Violation/Deviations and Serious Breaches will be followed.

## 8. ASSESSMENT AND FOLLOW-UP

### 8.1 SCREENING ASSESSMENTS

All children aged between 1 and 5 years attending the out-patient clinic for reported recurrent wheeze will be eligible. No additional initial screening assessments will be made other than to ensure the child meets the inclusion and exclusion criteria outlined in Section 4.2 and 4.3 above.

### 8.2 BASELINE ASSESSMENTS

At the clinic appointment parents of eligible children will be approached and will be verbally informed about the study and given a written information sheet. Parents' contact details will be taken and after a few days will be telephoned to ask whether they would like to take part in the study. Once parents have agreed, they will be invited for a research visit for baseline assessments prior to randomisation.

As wheezing in preschool children is a seasonal disorder (main symptoms between September – April each year), the baseline assessments and pre-randomisation visits will be arranged between late August – December each year, so that randomisation and intervention take place between September – January each year, to allow the 4 month intervention period to fall in the main season.

All baseline assessments will be made providing the child has not had any acute wheezing episodes within the last 2 weeks. Also, with their Consultant's permission, parents will be asked to stop administering any regular inhaled steroids (if they have been taking them) for 2 weeks prior to the research visit.

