## **3. STUDY DESIGN**

This is a single blind, randomised, controlled trial comparing management of moderate to severe preschool wheeze according to current clinical guidelines to management determined by inflammation and infection profile (pathological phenotype).

**Study duration:** The intervention phase of the study will last for 4 months, with follow-up immediately after the intervention period and 6 monthly thereafter until the end of the trial. The minimum follow-up is at the end of the 4 month intervention period, maximum follow-up will be for 3 years. During the 4 month intervention period, families will be contacted weekly by phone call for an update on unscheduled healthcare visits and symptoms.

**Type of subjects to be recruited:** All subjects will be aged between 1 and 5 years old. All subjects will have moderate to severe preschool wheeze, defined as  $\geq 2$  oral steroid bursts OR hospital admissions for acute wheeze in the last 12 months, with at least one oral steroid burst OR hospital admission in the last 6 months.

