#### **4. PARTICIPANT ENTRY**

Patient recruitment at a site will only commence once the trial team has ensured that the following approval/essential documents are in place:

1. The main REC, and Clinical Trial Authorization (CTA) approval,
2. Final sponsorship and/or R&D approval (NHS Permission),
3. Sponsor has conducted the trial initiation procedure

Patient identification will take place at up to 5 sites (Royal Brompton Hospital, Kings College Hospital, Chelsea & Westminster Hospital, St Mary's Hospital and Hillingdon Hospital, London), all research visits, screening assessments, randomisation and drugs will be dispensed from the Brompton Hospital only. Kings College Hospital, Chelsea & Westminster Hospital, St Mary's Hospital and Hillingdon Hospital will be used as patient identification (PIC) sites.

All sites participating in the trial will also be asked to provide a copy of the following:

1. Host site (R&D approval) and/or NHS Permission

All subjects who wish to enter the study will be fully screened and consented by the Chief Investigator, or one of the qualified clinicians involved in the study as Clinical Co-investigator.

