## 5. RANDOMISATION AND ENROLMENT PROCEDURE

### 5.1 Randomisation practicalities

All randomisation and enrolment will occur during routine working hours – as all research visits will take place in the Biomedical Research Unit during the week between 9am and 5pm. Children will be recruited when they are clinically well, not during an acute attack.

We will use the Imperial INFORM database Unit to undertake randomisation

We wish to stratify randomisation according to sex and age, to achieve similar numbers of boys and girls in each group, and to have a similar average age for each group.

The age stratification will be as follows: >1-  $\leq$ 3 years and >3 -  $\leq$ 5 years

As wheezing in preschool children is a seasonal disorder (majority of symptoms and exacerbations occur between September – April each year), the baseline assessments and pre-randomisation visits will be arranged between late August – December each year, so that randomisation and intervention take place between September – January each year, to allow the 4 month intervention period to fall within the main season.

All patients will be given a study specific 24hrs emergency contact card immediately after being randomised. The card includes details of the study: Study title, patient trial number, CI/PI's contact details along with out of hours contact details in case of emergency.

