### **8.4 SUBSEQUENT ASSESSMENTS**

Children will not routinely be brought back for follow-up during the 4 month intervention period.

Their compliance with the treatment prescribed will be monitored using electronic monitoring devices for the inhaled treatment, and by weekly telephone calls by the research nurse to remind the family of the importance of making sure the treatment is given daily for the period prescribed.

A symptoms diary will not be kept by the parents during the intervention period, but an automated text will be sent to the parents daily asking whether or not their child had any

symptoms of wheeze in the last 24 hours – the answer to the text will be a simple “yes” or “no” response.

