**8.5 LOSS TO FOLLOW-UP**

All attempts will be made to stay in touch with families, initially weekly phonecalls will be undertaken during the intervention period to stay in touch, and subsequently, even if they do not wish to attend the hospital for follow-up visits, information will be obtained by phone call about symptoms, medication and unscheduled healthcare visits. If a family cannot be contacted, the GP and local hospital will be contacted to determine any change of address.

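### The 24-hour emergency card is issued only after randomisation, so it does not cover the 2-week stop of inhaled steroids that the trial requests beforehand (minor, cheap to fix)

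*Combined protocol and SAP*

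**What the plan says.** Section 8.2 (Baseline assessments) sets out the sequence before randomisation. Families are told about the study in clinic and given an information sheet. They are telephoned some days later and, if willing, invited to a research visit that precedes randomisation. For children already on regular inhaled steroids, "with their Consultant's permission, parents will be asked to stop administering any regular inhaled steroids". The stop lasts 2 weeks and ends at that visit. The same section makes the baseline assessments conditional on no acute wheeze in the preceding 2 weeks.

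The children concerned have recent severe disease. Section 3 requires at least two oral steroid courses or admissions in a year, "with at least one oral steroid burst OR hospital admission in the last 6 months".

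On emergency contact, section 5.1 says: "All patients will be given a study specific 24hrs emergency contact card immediately after being randomised". It describes the contents as follows: "The card includes details of the study: Study title, patient trial number", together with investigator and out-of-hours contact details.

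Section 4.4 adds that a child who becomes ill should be seen in the usual way and that the study does not influence acute management. The Study Summary (Design) describes a proof of concept study meant to establish feasibility and supply data for sizing a larger trial.

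**The concern.** Stopping a regular preventer in a child with recent attacks is a treatment change made at the trial's request and for the trial's purposes. Parents who are worried during those 2 weeks are the people an emergency card is meant to serve, yet the stated rule gives it to them later.

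The protocol does provide the card for a comparable change. Under section 6.1, children in the pathological phenotype arm without eosinophilic inflammation who were on inhaled steroids are asked to stop them for 4 months. That stop follows randomisation, so the card is already in the parents' hands.

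There is also a feasibility question. Some children may start the stop and never be randomised. A larger trial using the same run-in would want to know how many and why, and the protocol does not provide for counting them.

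**Working it through.** The plan gives no figure to reproduce here. The check is one of timing, followed by a reading of the records the protocol names.

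**Timing.** Take the research visit as day 0.

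- Start of the stop: day −14 (section 8.2, 2 weeks before the visit).
- Research visit: day 0 (section 8.2, before randomisation).
- Randomisation: day d, with d ≥ 0. The protocol does not give d.
- Card issued: day d, straight after randomisation (section 5.1).

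Interval from the start of the stop to the card = d − (−14) = 14 + d days, so at least 14 days. Days of the stop covered by the card = 0 of 14, whatever d is.

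**Can a child start the stop and not be randomised?** Yes, by at least two routes in the text.

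1. Acute wheeze in the 2 weeks before the visit holds back the baseline assessments (section 8.2). That window is the same 2 weeks as the stop. The section does not say whether the child then resumes steroids, repeats the stop or leaves the study.
2. Section 3 (Number of subjects) counts a child as evaluable only if blood and an oropharyngeal swab are obtained before randomisation. A child may complete the stop and fail on this.

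**Does any named record count such children?** The protocol names four.

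- The CRF with the Sponsor's AE Log (section 7): adverse events, with no start date given.
- The Sponsor's log of deviations, breaches and urgent safety measures (section 7).
- The pharmacy accountability log (section 6.5).
- The delegation log (section 11.3).

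None is described as listing children who began the stop and were not randomised, and no screening log is mentioned.

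**How many cards would move earlier?** The share of children on regular inhaled steroids at recruitment is not given. Assume 25% to 100%.

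- With 72 children: 0.25 × 72 = 18, up to 72.
- With 100 children: 0.25 × 100 = 25, up to 100.

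These are cards the trial would issue anyway, only sooner. The extra ones are one per child who starts the stop and is not randomised, a number the documents do not allow us to estimate.

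**Does the stop affect the comparison?** It takes place before allocation, under a rule that cannot depend on the arm. It may affect who reaches randomisation, but it does not favour either arm.

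**The case against.** The case on the other side accepts the timing and disputes its weight. Several parts of it stand.

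**Unseen documents.** Parents receive an information sheet before the stop, and consent and contact pages were not available for this review. The sheet may well carry a telephone number and advice. This limits the point to what section 5.1 says about the card. It does not show that parents have nobody to call.

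**Existing protections.** The stop needs the Consultant's permission, children are recruited when well (section 5.1), and usual acute care applies (section 4.4). These lower the risk. They do not replace a trial contact: permission is given at the start, and usual care depends on the parent presenting the child.

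**Adverse event records.** Section 7 asks for all adverse events to be recorded and defers to a Sponsor SOP that was not seen. An event during the stop in a consented child might be captured. A reader might therefore go too far in concluding that these children will go uncounted. The documents support only that no count is specified. Even so, an event log would not list a child who stopped steroids, had no event and dropped out.

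**Calls and texts.** A reader might infer that the lack of calls and texts during the stop is also missing safety cover. The documents do not support that. Section 3 says "During the 4 month intervention period, families will be contacted weekly by phone call" to obtain updates on healthcare visits and symptoms. Sections 6 and 8.4 use the calls to encourage adherence, and section 8.5 says "initially weekly phonecalls will be undertaken during the intervention period to stay in touch". In section 8.4 no symptom diary is kept "during the intervention period, but an automated text will be sent to the parents daily". These contacts serve outcome capture, adherence and retention in the intervention period, so they naturally start with it. Adding calls or a record of attacks during the stop would be a preference. It might also gather health data before consent is signed, because the protocol does not say when consent is signed relative to the stop.

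**Conclusion.** The point holds as a minor one. The only emergency contact described in the protocol reaches families at least 14 days after the trial asks them to stop a regular treatment, and covers none of the 14 days of that stop. No count is specified of children who start the stop but are not randomised.

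This rests on the card being the only emergency contact the protocol describes, and on the research visit preceding randomisation as section 8.2 states. If the information sheet already gives an out-of-hours number and advice on worsening, what remains is mainly the count.

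Two stronger conclusions should not be drawn. A reader might infer that the stop harms children. The documents give neither the share on inhaled steroids nor any attack rate on and off them, so no excess risk can be derived. A reader might also infer a threat to the trial result. The stop precedes randomisation in both arms and does not bias the comparison.

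The timing of consent relative to the stop, and the start of adverse event recording, are unstated. Neither is shown to be wrong.

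**What to change.** Amend sections 5.1 and 8.2 as follows.

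1. Issue the 24-hour card when the stop begins. Section 5.1 puts the trial number on the card, so use a screening number if none has been assigned.
2. Add one line for parents: if the child worsens, seek care in the usual way and ask the child's own clinician about restarting inhaled steroids. This leaves the decision with the treating clinician and is consistent with section 4.4.
3. Keep a simple count of children who start the stop but are not randomised, with the reason, and report it with the feasibility results.

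The cost is a short amendment and a brief tally. Cards must reach families before the visit. Section 4 says "all research visits, screening assessments, randomisation and drugs will be dispensed from the Brompton Hospital only", while children may be identified at up to five hospitals, so cards would have to be sent out or handed over where the child is identified. Some children who are never randomised will have to be accounted for. Randomisation, outcomes and analysis do not change.
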